## Neurological Adverse Event Management Algorithm

Rule out non-inflammatory causes. If non-inflammatory cause, treat accordingly and continue I-O therapy.

Patients on IV steroids may be switched to an equivalent dose of oral corticosteroids (e.g. prednisone) at start of tapering or earlier, once sustained clinical improvement is observed. Lower bioavailability of oral corticosteroids should be taken into account when switching to the equivalent dose of oral corticosteroids.

27-Jun-2018

## APPENDIX 2 WOMEN OF CHILDBEARING POTENTIAL DEFINITIONS AND METHODS OF CONTRACEPTION

### DEFINITIONS

#### Woman of Childbearing Potential (WOCBP)

A woman is considered fertile following menarche and until becoming post-menopausal unless permanently sterile. Permanent sterilization methods include hysterectomy, bilateral salpingectomy, and bilateral oophorectomy.

#### Women in the following categories are not considered WOCBP

- Premenarchal
- Premenopausal female with 1 of the following:
  - Documented hysterectomy
  - Documented bilateral salpingectomy
  - Documented bilateral oophorectomy

Note: Documentation can come from the site personnel's review of the participant's medical records, medical examination, or medical history interview.

- Postmenopausal female
  - A postmenopausal state is defined as 12 months of amenorrhea in a woman over age 45 years in the absence of other biological or physiological causes. In addition, females under the age of 55 years must have a serum follicle stimulating hormone, (FSH) level > 40 mIU/mL to confirm menopause.

### CONTRACEPTION GUIDANCE FOR FEMALE PARTICIPANTS OF CHILD BEARING POTENTIAL

One of the highly effective methods of contraception listed below is required during study duration and until the end of relevant systemic exposure, defined as 5 months after the end of study treatment for female participants of childbearing potential treated with nivolumab plus ipilimumab, and 5 half-lives plus 30 days, or the duration specified by the local labels of chemotherapy drugs received, whichever is longer.

Local laws and regulations may require use of alternative and/or additional contraception methods.

Highly Effective Contraceptive Methods That Are User Dependent
---

Failure rate of <1% per year when used consistently and correctly.a
--

- |   |
|---|
| 

• Combined (estrogen- and progestogen-containing) hormonal contraception associated with inhibition of ovulationb

– oral

– intravaginal

– transdermal

 |
|---|

 
• Progestogen-only hormonal contraception associated with inhibition of ovulationb 
 
– oral
 
– injectable
 
 
 

Highly Effective Methods That Are User Independent

 
• Implantable progestogen-only hormonal contraception associated with inhibition of ovulationb
 
• Intrauterine hormone-releasing system (IUS)c
 
• Intrauterine device (IUD)c
 
• Bilateral tubal occlusion
 

 
• Vasectomized partner
 
 
A vasectomized partner is a highly effective contraception method provided that the partner is the sole male sexual partner of the WOCBP and the absence of sperm has been confirmed. If not, an additional highly effective method of contraception should be used.


 
• Sexual abstinence
 
 
Sexual abstinence is considered a highly effective method only if defined as refraining from heterosexual intercourse during the entire period of risk associated with the study drug. The reliability of sexual abstinence needs to be evaluated in relation to the duration of the study and the preferred and usual lifestyle of the participant.
 
 
• It is not necessary to use any other method of contraception when complete abstinence is elected.
 
• WOCBP participants who choose complete abstinence must continue to have pregnancy tests, as specified in Section 2.
 
• Acceptable alternate methods of highly effective contraception must be discussed in the event that the WOCBP participants chooses to forego complete abstinence
 

NOTES:
 
a Typical use failure rates may differ from those when used consistently and correctly. Use should be consistent with local regulations regarding the use of contraceptive methods for participants participating in clinical studies.
 
b Hormonal contraception may be susceptible to interaction with the study drug, which may reduce the efficacy of the contraceptive method. Hormonal contraception is permissible only when there is sufficient evidence that the IMP and other study medications will not alter hormonal exposures such that contraception would be ineffective or result in increased exposures that could be potentially hazardous. In this case, alternative methods of contraception should be utilized.
 
c Intrauterine devices and intrauterine hormone releasing systems are acceptable methods of contraception in the absence of definitive drug interaction studies when hormone exposures from intrauterine devices do not alter contraception effectiveness

Unacceptable Methods of Contraception

 
• Male or female condom with or without spermicide. Male and female condoms cannot be used simultaneously
 
• Diaphragm with spermicide
 
• Cervical cap with spermicide
 

- Vaginal Sponge with spermicide
- Progestogen-only oral hormonal contraception, where inhibition of ovulation is not the primary mechanism of action
- Periodic abstinence (calendar, symptothermal, post-ovulation methods)
- Withdrawal (coitus interruptus).
- Spermicide only
- Lactation amenorrhea method (LAM)

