## **1.4.2 Summary of Clinical Pharmacology**

### **1.4.2.1 Nivolumab**

The pharmacokinetics (PK) of nivolumab was studied in subjects over a dose range of 0.1 to 20 mg/kg administered as a single dose or as multiple doses of nivolumab every 2 or 3 weeks. Based on a population pharmacokinetic (PPK) analysis using data from patients with various tumor types, including melanoma, NSCLC, and RCC and a time varying CL model, nivolumab clearance was shown to decrease over time, with a median maximal reduction from baseline values of approximately 25% resulting in a geometric mean steady state clearance (CLss) (% coefficient of variation [CV%]) of 8.2 mL/h [53.9%]. The decrease in CLss is not considered to be clinically relevant. The geometric mean [CV%] volume of distribution at steady state (Vss) is 6.8 L (27.3%), and elimination half-life (t1/2) is 25 days (77.5%). Steady-state concentrations of nivolumab were reached by approximately 12 weeks when administered at 3 mg/kg every 2 weeks, and systemic accumulation was approximately 3.7-fold. The exposure to nivolumab increased dose proportionally over the dose range of 0.1 to 10 mg/kg administered every 2 weeks. The clearance of nivolumab increased with increasing body weight. The PPK analysis suggested that the following factors had no clinically important effect on the clearance of nivolumab: age (29 to 87 years), gender, race, baseline LDH, PD-L1, solid tumor type, baseline tumor size, and hepatic impairment. Although ECOG status, baseline glomerular filtration rate (GFR), albumin, and body weight had an effect on nivolumab CL, the effect was not clinically meaningful. PPK analysis suggested that nivolumab CL in subjects with cHL was approximately 32% lower relative to subjects with NSCLC; however, the lower CL in cHL subjects was not considered to be clinically relevant as nivolumab exposure was not a significant predictor for safety risks for these patients. When nivolumab is administered in combination with ipilimumab, the CL of nivolumab was increased by 24%, whereas there was no effect on the clearance of ipilimumab. Additionally, PPK and exposure response analyses have been performed to support use of 240 mg Q2W dosing in addition to the 3 mg/kg Q2W regimen. Using the PPK model, exposure of nivolumab at 240 mg flat dose was identical to a dose of 3 mg/kg for subjects weighing 80 kg, which was the approximate median body weight in nivolumab clinical trials (see [Section 1.1.5](#)). Additional details are provided in the investigator brochure.

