      - viii) Total Bilirubin  $\leq 1.5 \times \text{ULN}$  (except subjects with Gilbert Syndrome who must have a total bilirubin level of  $< 3.0 \times \text{ULN}$ )
- **Age and Reproductive Status**
  - d) Males and Females  $\geq 18$  years of age

- e) WOCBP must have a negative serum or urine pregnancy test (minimum sensitivity 25 IU/L or equivalent units of HCG) within 24 hours prior to the start of study drug.
- f) Women must not be breastfeeding
- g) WOCBP randomized to the nivolumab -plus -ipilimumab arm or the nivolumab-plus-chemotherapy arm must agree to follow instructions for method(s) of contraception for the duration of study treatment and 5 months after the last dose of study treatment (i.e., 30 days [duration of ovulatory cycle] plus the time required for the investigational drug to undergo approximately five half-lives).
- h) Males randomized to the nivolumab plus ipilimumab arm or the nivolumab-plus-chemotherapy arm and who are sexually active with WOCBP must agree to follow instructions for method(s) of contraception for the duration of study treatment and 7 months after the last dose of study treatment (i.e., 90 days [duration of sperm turnover] plus the time required for the investigational drug to undergo approximately five half-lives). In addition, male subjects must be willing to refrain from sperm donation during this time.
- i) WOCBP randomized to the chemotherapy arms must also agree to follow instructions for method(s) of contraception from the time of enrollment for the duration of treatment with chemotherapy plus 5 half-lives of chemotherapy plus 30 days (duration of ovulatory cycle) or a duration specified by the local labels of the chemotherapy drugs received, whichever is longer.
- j) Males randomized to the chemotherapy arms who are sexually active with WOCBP must also agree to follow instructions for method(s) of contraception for the duration of treatment with chemotherapy plus 5 half lives of chemotherapy plus 90 days (duration of sperm turnover) or a duration specified by the local labels of the chemotherapy drugs received, whichever is longer. In addition, male subjects must be willing to refrain from sperm donation during this time. Azoospermic males are exempt from contraceptive requirements. WOCBP who are continuously not heterosexually active are also exempt from contraceptive requirements, and still must undergo pregnancy testing as described in this section.

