### **6.4 Pregnancy**

If, following initiation of the study drug, it is subsequently discovered that a study subject is pregnant or may have been pregnant at the time of study exposure, including during at least 5 half lives after product administration, the investigator must immediately notify the Sponsor or designee of this event and complete and forward a Pregnancy Surveillance Form to BMS Designee within 24 hours of awareness of the event and in accordance with SAE reporting procedures described in [Section 6.1.1](#).

In most cases, the study drug will be permanently discontinued in an appropriate manner (eg, dose tapering if necessary for subject safety). Please call the Sponsor or designee within 24 hours of awareness of the pregnancy.

The investigator must immediately notify the Sponsor or designee of this event and complete and forward a Pregnancy Surveillance Form to Sponsor or designee within 24 hours of awareness of the event and in accordance with SAE reporting procedures described in [Section 6.1.1](#).

Follow-up information regarding the course of the pregnancy, including perinatal and neonatal outcome and, where applicable, offspring information must be reported on the Pregnancy Surveillance Form.

Any pregnancy that occurs in a female partner of a male study participant should be reported to Sponsor or designee. In order for BMS to collect any pregnancy surveillance information from the female partner, the female partner must sign an informed consent form for disclosure of this information. Information on this pregnancy will be collected on the Pregnancy Surveillance Form.

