### **CONTRACEPTION GUIDANCE FOR MALE PARTICIPANTS WITH PARTNER(S) OF CHILD BEARING POTENTIAL.**

Male participants with female partners of childbearing potential are eligible to participate if they agree to the following during the treatment and until the end of relevant systemic exposure.

- Inform any and all partner(s) of their participation in a clinical drug study and the need to comply with contraception instructions as directed by the investigator.
- Male participants are required to use a condom for study duration and until end of relevant systemic exposure defined as 7 months after the end of study treatment if treated with nivolumab plus ipilimumab, and 5 half-lives plus 90 days or a duration specified by local labels of chemotherapy, whichever is longer.
- Female partners of males participating in the study to consider use of effective methods of contraception until the end of relevant systemic exposure as defined above.
- Male participants with a pregnant or breastfeeding partner must agree to remain abstinent from penile vaginal intercourse or use a male condom during each episode of penile penetration during the treatment and until the end of relevant systemic exposure as defined above.
- Refrain from donating sperm for the duration of the study treatment until the end of relevant exposure period defined as: 7 months after the end of study treatment if treated with nivolumab plus ipilimumab, and 5 half-lives plus 90 days or a duration specified by local labels of chemotherapy, whichever is longer.

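### Appendix 2 ties the 5- and 7-month contraception periods to nivolumab plus ipilimumab only and leaves out the nivolumab-plus-chemotherapy arm, which the inclusion criteria hold to the same periods

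*Protocol*

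**What the plan says.** Section 3.3.1 sets the durations by arm. Criterion (g) covers both nivolumab arms: "WOCBP randomized to the nivolumab -plus -ipilimumab arm or the nivolumab-plus-chemotherapy arm must agree to follow instructions for method(s) of contraception", for 5 months after the last dose. Criterion (h) does the same for men, "Males randomized to the nivolumab plus ipilimumab arm or the nivolumab-plus-chemotherapy arm and who are sexually active with WOCBP must agree", for 7 months, with no sperm donation in that time. Criteria (i) and (j) then add a chemotherapy rule for subjects in the chemotherapy arms. For women it runs "for the duration of treatment with chemotherapy plus 5 half-lives of chemotherapy plus 30 days", or the local label period if longer; for men the added time is 90 days.

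Appendix 2 restates the durations three times:

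- **Women:** "defined as 5 months after the end of study treatment for female participants of childbearing potential treated with nivolumab plus ipilimumab".
- **Men, condom use:** "7 months after the end of study treatment if treated with nivolumab plus ipilimumab".
- **Men, sperm donation:** "Refrain from donating sperm for the duration of the study treatment until the end of relevant exposure period defined as: 7 months", again conditional on nivolumab plus ipilimumab.

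The only other duration in each statement is five half-lives and a further 30 days (90 for men), or the local chemotherapy label period, whichever is longer. The statements do not say whose half-lives are meant, and nivolumab plus chemotherapy appears in none of them.

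**The concern.** Arm B receives nivolumab every two weeks, so subjects leaving treatment in Arm B carry the same drug as those in Arm A. Appendix 2 sets its standard as the end of relevant systemic exposure, but it assigns the nivolumab-length periods to one of the two nivolumab arms. A site using the appendix alone could tell an Arm B woman to stop contraception, or an Arm B man to resume sperm donation, before nivolumab has cleared.

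Two further items in the male guidance, on partners' contraception and on pregnant or breastfeeding partners, refer back to the same definition and inherit the gap. Routine testing may not catch the consequence. Table 5.1-5 schedules the follow-up pregnancy test at the first follow-up visit only, normally about 30 days after the last dose, unless local rules ask for more.

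Section 6.4 treats exposure in pregnancy as possible "including during at least 5 half lives after product administration", a window that for nivolumab runs well past that visit.

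**Working it through.** **Inputs from the Protocol**

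- Nivolumab half-life: 25 days (Section 1.4.2.1).
- Ipilimumab half-life: 15.4 days (Section 1.4.2.2).
- Rule behind criteria (g) and (h): five half-lives plus 30 days (women) or 90 days (men).
- 939 subjects randomized 1:1:1 (Section 3.1).
- From the SAP, Section 10: 1 month = 30.4375 days.

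**Assumption, not in the documents:** five chemotherapy half-lives total 0 to 10 days, and no longer local label applies.

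**Step 1. Reproduce the stated periods.**

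- Nivolumab, women: 30 + 5 × 25 = 155 days; 155 / 30.4375 = 5.09 months.
- Nivolumab, men: 90 + 5 × 25 = 215 days; 215 / 30.4375 = 7.06 months.
- Ipilimumab, women: 30 + 5 × 15.4 = 107 days, or 3.5 months.
- Ipilimumab, men: 90 + 5 × 15.4 = 167 days, or 5.5 months.

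Only nivolumab reproduces 5 and 7 months. Its half-life drives both periods, and the reason applies to Arm B as much as to Arm A.

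**Step 2. Compare coverage.**

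| Place | Arm A | Arm B |
|---|---|---|
| Criteria (g), (h) | 5 / 7 months | 5 / 7 months |
| Appendix 2, women | 5 months | not named |
| Appendix 2, condom use | 7 months | not named |
| Appendix 2, sperm donation | 7 months | not named |

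**Step 3. Size of the shortfall if Arm B falls to the chemotherapy clause.** Required: 5 × 30.4375 = 152 days and 7 × 30.4375 = 213 days.

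- Women: the clause gives 30 to 40 days. Shortfall 152 − 40 = 112 to 152 − 30 = 122 days.
- Men: the clause gives 90 to 100 days. Shortfall 213 − 100 = 113 to 213 − 90 = 123 days.

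**Step 4. Nivolumab remaining at those times.** With simple exponential decline from the last nivolumab dose, the fraction left at day *t* is 2^(−t/25).

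- Day 30: 0.435. Day 40: 0.330.
- Day 90: 0.082. Day 100: 0.0625.
- Day 152: 0.015. Day 213: 0.003.

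**Step 5. Section 6.4 window.** 5 × 25 = 125 days. It would end 125 − 40 = 85 to 125 − 30 = 95 days after the women's minimum, and 125 − 100 = 25 to 125 − 90 = 35 days after the men's.

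**Step 6. Who is affected.** Arm B has about 939 / 3 = 313 subjects. Those who are women of childbearing potential, or men with such partners, are a smaller number that the documents do not give.

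**The case against.** The strongest reply is that no requirement is missing. Criteria (g) and (h) bind Arm B explicitly, Section 3.3 insists that every eligibility criterion be met, and Section 3.3.1 points to Appendix 2 for contraceptive methods, not for how long to use them. Harm needs a site to rely on the appendix and overlook the criteria under which it enrolled the subject. This stands, and it limits the seriousness. It does not make the appendix correct, because the appendix does state durations.

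The appendix can also be read without a gap. Its half-lives are not attributed to a drug, and if they are nivolumab's the periods become 155 and 215 days. Criterion (i) uses the same formula and says the half-lives are those of chemotherapy, which favours the shorter reading, but the text is ambiguous.

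The size is uncertain. The chemotherapy half-lives and labels are not in the documents, and the Revised Protocol 02 change history says the chemotherapy rule was written to meet label requirements, so a label may well govern. The residual-drug figures use a single half-life although Section 1.4.2.1 gives a coefficient of variation of 77.5%. They also count from the last nivolumab dose, while Appendix 2 counts from the end of study treatment. Section 4.5.5.2 lets chemotherapy continue after nivolumab stops, and such subjects would have less drug left. These points are fair, so the Step 4 figures are illustrative. None of them removes the omission.

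**Conclusion.** The concern holds. As written, Appendix 2 disagrees with criteria (g) and (h) in three places by leaving out an arm that receives the drug on which the periods are based. The shortfall ranges from zero, if the local label is at least 5 or 7 months or the half-lives are taken as nivolumab's, to about 122 days for women and 123 days for men on the chemotherapy reading with no longer label. At that minimum roughly 33% to 44% of nivolumab would remain for women and 6% to 8% for men, subject to the simplifications noted above.

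This is an internal inconsistency with a patient-safety consequence for a limited group. It should be corrected, but the binding eligibility text already carries the right rule. What the consent form tells participants could not be checked. Sample size, endpoints and analyses are unaffected.

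**What to change.** In the female statement and in both male statements of Appendix 2, extend the 5- and 7-month periods to subjects treated with nivolumab plus ipilimumab or nivolumab plus chemotherapy. In the same sentences, specify that the five half-lives are those of chemotherapy. State that the chemotherapy or local-label rule applies in addition for Arms B and C, with the longer period governing. The two items that refer back to the definition are then corrected without further change.

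The cost is a wording change in three sentences, by protocol revision or administrative letter, and a notice to sites. It aligns the appendix with criteria (g) to (j) and adds no new requirement.

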### **CONTRACEPTION GUIDANCE FOR MALE PARTICIPANTS WITH PARTNER(S) OF CHILD BEARING POTENTIAL.**

Male participants with female partners of childbearing potential are eligible to participate if they agree to the following during the treatment and until the end of relevant systemic exposure.

- Inform any and all partner(s) of their participation in a clinical drug study and the need to comply with contraception instructions as directed by the investigator.
- Male participants are required to use a condom for study duration and until end of relevant systemic exposure defined as 7 months after the end of study treatment if treated with nivolumab plus ipilimumab, and 5 half-lives plus 90 days or a duration specified by local labels of chemotherapy, whichever is longer.
- Female partners of males participating in the study to consider use of effective methods of contraception until the end of relevant systemic exposure as defined above.
- Male participants with a pregnant or breastfeeding partner must agree to remain abstinent from penile vaginal intercourse or use a male condom during each episode of penile penetration during the treatment and until the end of relevant systemic exposure as defined above.
- Refrain from donating sperm for the duration of the study treatment until the end of relevant exposure period defined as: 7 months after the end of study treatment if treated with nivolumab plus ipilimumab, and 5 half-lives plus 90 days or a duration specified by local labels of chemotherapy, whichever is longer.

### **COLLECTION OF PREGNANCY INFORMATION**

Guidance for collection of Pregnancy Information and outcome of pregnancy on the Pregnancy Surveillance Form is provided in [Section 6.4](#) and the Appendix for Adverse Events and Serious Adverse Events Definitions and procedures for Evaluating, Follow-up and Reporting.

**APPENDIX 3 ECOG PERFORMANCE STATUS**

ECOG PERFORMANCE STATUS	
0	Fully active, able to carry on all pre-disease performance without restriction
1	Restricted in physically strenuous activity but ambulatory and able to carry out work of a light or sedentary nature, e.g., light house work, office work
2	Ambulatory and capable of all selfcare but unable to carry out any work activities. Up and about more than 50% of waking hours
3	Capable of only limited selfcare, confined to bed or chair more than 50% of waking hours
4	Completely disabled. Cannot carry on any selfcare. Totally confined to bed or chair
5	Dead

Source: Oken MM, Creech RH, Toney DC, Horton J, Davis TE, McFadden ET, and Carbone PP. Toxicity and Response Criteria of the Eastern Cooperative Oncology Group. Am J Clin Oncol 1982; 5: 649-655.

